3.2 Secondary Endpoint(s)

1. **Difference in SPID-24 scores** between treatment groups will be assessed across the first 24 hours post-dose using the number of randomized and treated subjects on NRS (0-10).
2. **Change from baseline** will be assessed at 2 hours post-dose using the number of randomized and treated subjects.
3. **Pain freedom** will be assessed using the number of evaluable subjects that report no pain at 2 hours post-dose. Pain will be measured on NRS (0-10).
4. **Onset of meaningful pain relief** will be assessed by the first nominal timepoint at which the pain on NRS (0-10) decreases by 30% from baseline.
5. **Onset of initial pain relief** will be assessed by the first nominal timepoint at which the pain on NRS (0-10) decreases by 1 point from baseline.
6. The **probability of requiring rescue medication** will be assessed using the number of subjects that take rescue medication within 24 hours after administration of study medication (rimegepant or placebo).

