9.4.3.2 Change from Baseline of Pain on NRS

The change from baseline of pain on NRS score at 2 hours post-dose will be analyzed with a generalized linear mixed effect model that includes subject as a random effect, the baseline NRS (0-10) value as a covariate, and fixed effects for treatment group, stratification factor (use of daily medications / oral devices to reduce the intensity of TMD symptoms), scheduled time point, and time point by treatment group interaction. Time points included in the model are nominally at 15, 30, 45, 60, 90 and 120 minutes post-dose. Repeated measurements within-subject will be modeled using an unstructured covariance structure for within-subject error. In the case that the model fails to converge, a Huynh-Feldt error structure will be attempted, followed by an AR(1) structure. Error degrees of freedom will be calculated using a Kenward-Roger approximation. The difference estimate (rimegepant - placebo), SE, 95% CI, and p-value will be reported for 2 hours post-dose.

Intercurrent events of use of a non-study rescue medication at or before 2 hours post-dose, or if a subject fails to log their pain score at any time after study drug is administered through 2 hours post-dose, will be handled in the same manner as they are for the primary endpoint.

9.4.3.3 *Pain Freedom at 2 Hours*

The number of subjects that are pain free at 2 hours post-dose will be analyzed after first imputing missing data at 2 hours to be failure (NC = F). Additionally, subjects who use rescue medication on or before assessment of pain at 2 hours will also be assigned as failures (RM = F). The analysis will be done using a stratified Cochran-Mantel-Haenszel (CMH) test after imputation is done, with the stratification factor as use of daily medications / oral devices to reduce the intensity of TMD symptoms.

9.4.3.4 *Time to Onset of Meaningful Pain Relief*

Time to onset of meaningful pain relief post-dose will be defined as the first nominal timepoint at which a 30% reduction of pain from baseline on NRS is achieved. This will be analyzed using Kaplan-Meier methods for a “time to event” analysis. Rimegepant will be compared to placebo using a log-rank test which will compare the survival distributions. Intercurrent events will be handled in the same manner as they are for the primary endpoint.

9.4.3.5 *Time to Onset of Initial Pain Relief*

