3.2.2 Secondary Objective Estimands

Table 2: Secondary Objective Estimands

1	Objective	To evaluate rimegepant compared with placebo on the time-weighted sum of pain intensity difference (SPID) from baseline scores for the first 24 hours post-dose (SPID-24).
	Efficacy Endpoint	Difference in SPID-24 scores between rimegepant and placebo assessed across the first 24 hours post-dose in treated subjects
	Summary	Same as that of primary estimand, with respect to time-weighted SPID-24.
	Intercurrent Events	Same as that of primary estimand.
2	Objective	To evaluate rimegepant compared to placebo on change from baseline on NRS (0-10) score at 2 hours post-dose.
	Efficacy Endpoint	Change from baseline in NRS score to 2 hours post-dose in treated subjects.
	Summary	Difference in change from baseline in the NRS score between the rimegepant and placebo groups using a generalized linear mixed effect model.

	Intercurrent Events	Same as that of primary estimand.
3	Objective	To evaluate rimegepant compared to placebo on the proportion of subjects that are pain free at 2 hours post-dose.
	Efficacy Endpoint	The percentage of treated subjects that report no pain at 2 hours post-dose
	Summary	The difference between the rimegepant and placebo group in the percentage of subjects who are pain-free at 2 hours post-dose, analyzed using Mantel-Haenszel risk estimation. The definition of “pain free” is a subject that reports a zero on their 2 hour post-dose NRS assessment.
	Intercurrent Events	1) Use of non-study rescue medications on or before two hours post-dose Composite strategy: Subjects who use rescue medication on or before assessment of pain at two hours are imputed as a failure. 2) Failure to report eDiary assessments at two-hours post-dose Composite strategy: Subjects with missing data at two hours post-dose are imputed as a failure. 3) All other intercurrent events: Treatment policy strategy: All available assessments on the subject are used regardless of other intercurrent events.
4	Objective	To evaluate rimegepant compared to placebo on time to onset of meaningful pain relief post-dose.
	Efficacy Endpoint	The time to first nominal timepoint at which pain on NRS (0-10) decreases by 30% from baseline in treated subjects.

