	Summary	Descriptive analysis by treatment group of the time to first nominal timepoint at which pain on NRS (0-10) decreases by 30% from baseline using Kaplan-Meier method. Meaningful pain reduction will be measured as a two-point reduction in NRS (0-10) score for subjects with a baseline pain score of 6, 7, or 8 and a 3 point reduction in NRS (0-10) score for subjects with a baseline pain score of 9 or 10.
	Intercurrent Events	1) Use of non-study rescue medications on or before onset of meaningful pain relief Composite strategy: Subjects who use rescue medication on or before onset of meaningful pain relief are censored at the time of rescue medication use. 2) Failure to report eDiary assessments. Composite strategy: Subjects who do not complete all post-dose assessment will be censored at the time of the last completed NRS pain assessment. 3) All other intercurrent events: Treatment policy strategy: All available assessments on the subject are used regardless of other intercurrent events.
5	Objective	To evaluate rimegepant compared to placebo on time to onset of initial pain relief post-dose.
	Efficacy Endpoint	The time to first nominal timepoint at which pain on NRS (0-10) decreases by 1 point from baseline in treated subjects.
	Summary	Descriptive analysis by treatment group of the time to first nominal timepoint at which pain on NRS (0-10) decreases by 1 point from baseline using the Kaplan-Meier method.

Intercurrent Events	Same as secondary endpoint # 4
---------------------	--------------------------------

6	Objective	To evaluate rimegepant compared to placebo on the probability of requiring rescue medication within 24 hours of initial treatment.
	Efficacy Endpoint	Percentage of treated subjects that use rescue medication within 24 hours after administration of study drug.
	Summary	The difference in the percentage of subjects that take study drug and then take rescue medication within 24 hours, analyzed using Mantel-Haenszel risk estimation.
	Intercurrent Events	Treatment policy strategy : All available assessments on the subject are used regardless of intercurrent events.

CCI [REDACTED]

[REDACTED]

[REDACTED]

[REDACTED]

[REDACTED]

[REDACTED]

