5 SAMPLE SIZE, POWER, AND TYPE I ERROR

If 80% of the 200 randomized (100 per treatment arm) treat with study drug, we expect roughly 160 total or 80 per treatment group in the randomized and treated population for analysis.

Assuming rimegepant provides a 2-point reduction in NRS pain, and a 1.5-point advantage over placebo on the primary endpoint, and a common standard deviation of 3.0, then the study will have roughly 88% power on the primary endpoint.

Type 1 error is not applicable. The significance of the primary and secondary endpoints will not be evaluated.

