The pain intensity difference at each post-baseline timepoint (PID_i) is calculated by finding the difference between the NRS score at each timepoint (PI_i) from the baseline NRS score (PI_0).

$$PID_i = PI_i - PI_0$$

The SPID-2 will be calculated by multiplying the PID score at each post-dose timepoint by the duration (in hours) since the preceding timepoint, then summing the values over the 2 hours.

$$SPID - 2 = \sum_{i=1}^6 (T_i - T_{(i-1)}) * PID_i$$

Where $T_0 = 0$, T_i = the nominal time as described in Table 3, $T_{(i-1)}$ = the preceding nominal time, PID_i = PID score at time T_i

Table 3: NRS Collection Nominal Timepoints

NRS collection timepoint	i	T_i (hours)
15 minutes	1	0.25
30 minutes	2	0.50
45 minutes	3	0.75
60 minutes	4	1.00
90 minutes	5	1.50
2 hours	6	2.00
4 hours	7	4.00
8 hours	8	8.00
24 hours	9	24.00

The SPID-2 will be analyzed on the treated population using an analysis of covariance (ANCOVA) model, estimated by Restricted Maximum Likelihood (REML) that includes baseline NRS value as a covariate and treatment group and stratification factor (use of daily medications / oral devices to reduce the intensity of TMD symptoms) as the main effects. The least squares mean (LS mean), standard error (SE), and 95% confidence intervals (CI) for each treatment group will be estimated and reported, as well as the LS mean, SE, and 95% CI for the difference between treatment groups (rimegepant – placebo). Descriptive summaries of PID value at each measured timepoint will be presented by treatment group to include mean, SD, median, minimum, and maximum.

The intercurrent events of non-study rescue medication and failure to log NRS pain score are treated with a composite strategy. All assessments after rescue medication administration are set to the last observation prior to the time of rescue medication use. Any missing NRS assessment(s) will be imputed to the last non-missing observation prior to the missing assessment. For clarity, in the case of intermittent missing values, missing values will be imputed based on the last non-missing observation prior to the missing value or consecutive series of missing values; any subsequent non-missing values will not be imputed unless rescue medication was administered prior to that assessment. Subjects who mistakenly dose and thus have a missing baseline NRS assessment will have the missing baseline assessment imputed as the mean of the non-missing baseline assessments across subjects.

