6.3.3.3 Pain Freedom at 2 Hours

The number and percentage of subjects in the treated population that experience pain freedom at 2 hours post-dose are analyzed after first imputing missing data at 2 hours to be failure (NC [Non-completer] = F [Failure]). Additionally, subjects who use rescue medication on or before assessment of pain at 2 hours are also assigned as failures (RM [Rescue medication use] = F). If the time of first rescue medication is missing, subjects are considered as failures if the date of rescue medication is the same as the date of dosing.

The analysis is done using Mantel-Haenszel risk estimation after imputation is done, with the stratification factor as yes/no for use of daily medications / oral devices to reduce the intensity of TMD symptoms. If one category of stratification factor has sparse data (less than 5 subjects), then the stratification factor is removed. Pain freedom is defined as an NRS score of zero at 2 hours post-dose (yes or no).

Results presented from the analysis includes the following:

- Response rate (i.e., “n/N” and percentage), asymptotic standard error (ASE), and 95% CI by randomization stratum for each treatment group
- Response rate (i.e., “n/N” and percentage), ASE, and 95% CI for each treatment group
- Percentage difference between treatment groups (rimegepant – placebo), ASE and 95% CI by randomization stratum
- Stratified percentage difference between treatment groups (rimegepant – placebo), ASE and 95% CI

A forest plot is produced depicting the risk difference for pain freedom at 2 hours post dose. The risk difference for each stratum will be presented, as well as the overall common risk difference.

6.3.3.4 *Time to Onset of Meaningful Pain Relief*

Time to onset of meaningful pain relief post-dose is analyzed descriptively for the treated population using Kaplan-Meier methods. Meaningful pain relief is considered the event in these analyses and is defined as the first nominal timepoint at which a 30% reduction of pain from baseline on the NRS is achieved. For clarity, meaningful pain relief is a 2-point reduction in NRS (0-10) score for subjects with a baseline pain score of 6, 7, or 8, and a 3-point reduction in NRS (0-10) score for subjects with a baseline pain score of 9 or 10.

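### The SAP's whole-point cut-offs for meaningful pain relief accept drops of 28.6% (baseline 7) and 25.0% (baseline 8), although the endpoint is defined as a 30% reduction

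*SAP*

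**What the plan says.** Both documents define the event as a percentage. Protocol 3.2 takes "the first nominal timepoint at which the pain on NRS (0-10) decreases by 30% from baseline", and Protocol 9.4.3.4 takes "the first nominal timepoint at which a 30% reduction of pain from baseline on NRS is achieved". The protocol gives no whole-point cut-offs.

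SAP 3.2.2, Table 2, objective 4 keeps the percentage as the efficacy endpoint: "The time to first nominal timepoint at which pain on NRS (0-10) decreases by 30% from baseline in treated subjects". SAP 6.3.3.4 does the same, with the event "defined as the first nominal timepoint at which a 30% reduction of pain from baseline on the NRS is achieved".

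The SAP then converts the percentage to points. As a clarification, 6.3.3.4 says that "meaningful pain relief is a 2-point reduction in NRS (0-10) score for subjects with a baseline pain score of 6, 7, or 8", and requires 3 points at baselines 9 and 10. The summary row of Table 2, objective 4 repeats this with a "two-point reduction in NRS (0-10) score for subjects with a baseline pain score of 6, 7, or 8".

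Two other provisions matter here. Under SAP 6.3.2.1, subjects who dosed by mistake and have no baseline score get one "imputed as the mean of the non-missing baseline assessments across subjects"; SAP 7.5 repeats this. SAP section 5 states: "The significance of the primary and secondary endpoints will not be evaluated".

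**The concern.** A clarification should apply a definition, and this one loosens it for two of the five qualifying baseline scores. A programmer who codes the percentage and one who codes the cut-offs would get different results from the same data whenever a subject goes from 7 to 5, or from 8 to 6, before reaching a larger drop.

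For a descriptive endpoint, the event counts, Kaplan-Meier curve, median and quartiles are the result. Reported as time to a 30% reduction, they would include subjects who had not reached 30%.

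There is also a smaller gap. The cut-offs are listed only for baselines 6, 7, 8, 9 and 10. A mean-imputed baseline need not be a whole number, and no whole-point cut-off is given for that case.

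**Working it through.** **Inputs**
- NRS is recorded in integers from 0 to 10 (SAP 6.3.2.1).
- A qualifying score is 6 or more (SAP 6.2.6.1), so observed qualifying baselines b are 6 to 10.
- SAP cut-off c: 2 points for b = 6, 7, 8 and 3 points for b = 9, 10 (SAP 6.3.3.4 and Table 2).
- Threshold: 30%, read as 30% or more.

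**Formulas**
- Percentage implied by the SAP cut-off: 100 × c / b.
- Points needed for exactly 30%: 0.3 × b.
- Smallest integer drop reaching 30%: 0.3 × b rounded up.

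| Baseline b | SAP cut-off c | Implied reduction c/b | 0.3 × b | Smallest integer drop ≥ 30% | Its percentage |
|---|---|---|---|---|---|
| 6 | 2 (to NRS 4) | 33.3% | 1.8 | 2 | 33.3% |
| 7 | 2 (to NRS 5) | **28.6%** | 2.1 | 3 | 42.9% |
| 8 | 2 (to NRS 6) | **25.0%** | 2.4 | 3 | 37.5% |
| 9 | 3 (to NRS 6) | 33.3% | 2.7 | 3 | 33.3% |
| 10 | 3 (to NRS 7) | 30.0% | 3.0 | 3 | 30.0% |

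The cut-offs satisfy the definition at 6, 9 and 10. They miss it by 30 − 28.6 = 1.4 percentage points at 7 and by 30 − 25.0 = 5.0 points at 8.

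**Where the two rules disagree.** Over all integer pairs with baselines 6 to 10, the only disagreements are 7 to 5 and 8 to 6. In both, the cut-off counts an event and the percentage does not. There is no pair in the other direction.

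**Possible origin of the cut-offs.** Rounding 0.3 × b to the nearest integer turns 1.8, 2.1, 2.4, 2.7, 3.0 into 2, 2, 2, 3, 3, which reproduces all five.

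**Non-integer baselines.** As an assumed example, take an imputed baseline of 7.4 and a score of 5: (7.4 − 5)/7.4 = 32.4%, which reaches 30% with a 2.4-point drop. In general, a score of 5 reaches 30% for any baseline from 5/0.7 = 7.143 upward, and a score of 6 only from 6/0.7 = 8.571. So for imputed baselines from 7.143 to just under 8, the formula is met at a score of 5 with a drop of less than 3 points. A table that required 3 whole points there would not match the formula.

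**The case against.** The strongest defence is that an exact 30% drop is impossible on an integer scale at baselines 6, 7, 8 and 9, so some conversion was needed. Nearest-integer rounding explains every cut-off and gives the achievable percentage closest to 30%. A strict rule overshoots instead: 42.9% at baseline 7 and 37.5% at baseline 8, which is 12.9 and 7.5 points above 30%, against present shortfalls of 1.4 and 5.0. The current definitions also do not say at least 30%.

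Much of this stands. Rounding is a plausible origin, and keeping the cut-offs is a legitimate choice. It does not remove the contradiction: neither document states a rounding convention or calls 30% approximate, and on the ordinary reading a 25% fall does not achieve a 30% reduction. SAP 6.1.2 refers rounding rules to the Core SAP, which is not available here. Those rules may concern table display only, and nothing visible links them to this endpoint. The SAP's reference list includes a paper on minimal clinically important NRS changes, but no visible text ties it to the cut-offs either.

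The imputed-baseline gap is also narrower than it may look. The percentage definition can be applied to any baseline; only the whole-point version is missing. It matters only for mistaken dosers, whose number is unknown.

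Finally, the study stopped early for low enrolment, and SAP version 2.0 removed the log-rank comparison and all significance evaluation. That limits the consequence but does not reconcile the definitions.

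**Conclusion.** The concern holds. At baselines 7 and 8 the SAP's cut-offs accept reductions of 28.6% and 25.0% under an endpoint that both documents define as 30%. This rests on reading the definition as 30% or more.

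For observed baselines the direction is certain: more events, or earlier ones. The subjects affected are those with baseline 7 or 8 whose first pre-rescue drop of 2 or more points is exactly 2. The documents give no baseline distribution, so the size cannot be computed; it lies between zero and the share of treated subjects with baseline 7 or 8. Results at baselines 6, 9 and 10 are the same under both rules.

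The rule is identical in both arms, and no between-arm bias is claimed. No p-value and no primary result is affected. The contradiction should still be fixed, because it concerns what a protocol-named secondary endpoint measures.

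**What to change.** Change SAP 6.3.3.4 and Table 2, objective 4 in one of two ways.

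- **Align the scoring with the definition.** Score the event as (baseline − NRS)/baseline ≥ 0.30. For observed integer baselines this means at least 2 points at 6 and at least 3 points at 7, 8, 9 and 10. The formula also handles non-integer imputed baselines.
- **Keep the cut-offs and correct the label.** If 2 points at baselines 7 and 8 is deliberate, stop describing it as a 30% reduction, give the basis for the cut-offs (for example, rounding 0.3 × baseline to the nearest point, if that is what was done), state the departure from Protocol 3.2 and 9.4.3.4, and add a rule for non-integer baselines.

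The first option restores the protocol's endpoint, at the price of somewhat fewer and later events at baselines 7 and 8 and effective thresholds of 42.9% and 37.5% there. The second keeps the planned counts but reports a differently named endpoint. The first costs one sentence in two places and one line of code; the second costs slightly more text. Neither needs new data.

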6.4.2 Rescue Medication

The subject’s use of rescue medication is recorded by the subject in a paper diary.

CCI

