Time to onset of initial pain relief post-dose will be defined as the first nominal timepoint at which a 1-point reduction of pain from baseline on NRS is achieved. This will be analyzed using Kaplan-Meier methods for a “time to event” analysis. Rimegepant will be compared to placebo using a log-rank test which will compare the survival distributions. Intercurrent events will be handled in the same manner as they are for the primary endpoint.

9.4.3.6 *Rescue Medication Use through 24 Hours*

The number of subjects that use rescue medication through 24 hours post-dose will be analyzed using a stratified CMH test, with the stratification factor as use of daily medications/oral devices to reduce the intensity of TMD symptoms.

9.4.4 *Adjustment for Multiplicity*

Type 1 error is addressed in this study using a gatekeeping procedure. The significance of the primary endpoint is evaluated at the two-sided alpha level of 0.05. If the primary endpoint is significant, then the secondary endpoints are tested using Hochberg’s procedure.

CCI

9.4.5 *Missing Data*

For the primary and secondary endpoints of SPID-2, SPID-24, change in NRS from baseline, time to onset of meaningful pain relief, and time to onset of initial pain relief, subjects who fail to record their pain during the timeframe of interest for each endpoint will be considered

failures (NC = F) and this data will be imputed to the last available observation prior to the missing data occurrence.

For the secondary endpoint of proportion of subjects that are pain free at 2 hours post-dose, missing data at 2 hours post-dose will be imputed as a failure (NC = F), and these subjects will not be considered as having achieved pain freedom.

For the secondary endpoint of proportion of subjects who use rescue medication through 24 hours-post dose, there will be no imputation for missing data, the analysis will be based on non-missing, observed data.

Additional methods for handling of missing data, including sensitivity analyses, will be described in detail in the SAP.

9.4.6 *Rescue Medication*

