A by-subject listing is prepared that indicates the study drug exposure and accountability status for the treated analysis set; this listing includes study drug start date/time and study day, drug accountability kit dispensed date, kit returned date, kit ID, and IP used status (IP taken, IP not taken). A patient identifier listing is prepared if subjects had unknown exposure data, unknown accountability data, or for whom the exposure and accountability data did not match.

6.2.6.3 *Concomitant and Rescue Medications*

Concomitant non-study medications are tabulated by therapeutic class and preferred name for the treated analysis set. The definition of concomitant medication in Section 6.2.6.3 of the Core SAP, as applicable to single-dose studies, applies. For clarity, concomitant medications include

both medications recorded on the Concomitant Medications CRF that meet the definition of “concomitant” (see Section 6.2.6.3 of the Core SAP) and all rescue medications (defined below). Sites are instructed to exclude medications reported on the Rescue Medication CRF from the Concomitant Medications CRF.

Medications are displayed in descending order of overall frequency within therapeutic class and preferred name. Refer to the Sections 6.2.6.3 of the Core SAP for non-study medication counting rules in frequency tables.

Rescue medications include any non-study medication recorded on the Rescue Medication CRF with complete medication dates, and either (1) medication date/time is after the study drug start date/time if the medication time and study drug start time are both not missing, or (2) medication date is on or after study drug start date if the medication time or study drug start time is missing. Rescue medication dates are not imputed. Rescue medication times are not imputed, except as provided in Section 7.1.5 for time-to-event analyses. Rescue medications are separately tabulated and displayed in descending order of overall frequency within therapeutic class and preferred name for the treated analysis set. Any medication recorded on the Rescue Medication CRF that does not meet the above definition of a “rescue medication” will be treated as a current or concomitant medication, as appropriate, based on the imputed medication start date.

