The number and percentage of subjects that use rescue medication within 24 hours post-dose are analyzed. Subjects who used rescue medication as of 24 hours post-dose are deemed failures, and subjects who did not use rescue medication as of 24 hours are deemed successes. For clarity, failure is the event being modeled (i.e. rescue medication use within 24 hours) in this analysis.

Refer to Section 6.2.6.3 for the definition of rescue medication. A rescue medication would be deemed used as of 24 hours post-dose if the date/time of first rescue medication use is strictly } 24 hours after the date/time of dosing, notwithstanding Section 6.3.1 of the SAP. Subjects with a rescue medication start date on or before study drug start date/time + 24 hours and missing rescue medication start time are excluded. Subjects who report non-study medication on the Rescue Medication CRF with a missing rescue medication date, or a partial medication date that is consistent with being used within 24 hours of dosing, are also excluded. Regardless of the foregoing, if a subject has at least one rescue medication use with non-missing start time that is } 24 hours after the date/time of dosing, the subject will be included in the analyses and deemed a failure.

No analysis window around the 24-hour post-dose time point is used.

The analysis follows the same methodology set forth in Section 6.3.3.3. A forest plot is produced depicting the risk difference for rescue medication use within 24 hours post dose. The risk difference for each strata will be presented, as well as the overall common risk difference.

Time to rescue medication use through 24 hours post-dose is assessed by treatment group as follows:

- Kaplan-Meier plot and table using 2-hour time intervals (i.e., 0 to 2, > 2 to 4, ... , > 24). The Kaplan-Meier plot displays the percentage of subjects taking rescue medication

data without imputation and regardless of rescue medication use. In these tables of safety parameters, if a subject has multiple values in the end of treatment analysis visit window (see Section 7.3), then the last non-missing value measured in the analysis period is used. See Sections 6.3.4.1, 6.4.4.1, and 6.4.2.4 for further handling of ties on the same measurement date or time.

By-subject listings of safety parameters are described in subsections and identify on-treatment data.

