7.1.5 Other Derived/Imputed Dates

Additional derived dates include.

- Date/time of eDiary assessments: The date/time of a given assessment collected in the eDiary is the datetime the diary for that time point is saved (e.g., the date/time of all assessments collected on the 15 minute diary is the datetime the 15 minute diary is saved).
 - Rescue medication start date/time: Earliest rescue medication date/time. Missing time is considered to be earlier than non-missing time on the same date. Refer to Section 6.2.6.3.
-

- Imputed rescue medication start date/time: This is used **only** for time-to-event efficacy analyses in Section 6.3.3.5.
 - If the rescue medication start date and time are both not missing, then the imputed rescue medication start date/time is set to the rescue medication start date/time.
 - If the rescue medication start time is missing and the rescue medication start date is equal to the study drug dose date, then the imputed rescue medication start date/time is set to the study drug dose date/time.
 - Otherwise, if the rescue medication start time is missing and the rescue medication start date is equal to a post-dose eDiary finding date with non-missing efficacy data on that date (i.e., the day after dosing), then the imputed rescue medication start date/time is set to the first eDiary finding date/time on that date corresponding to non-missing efficacy data.
 - Otherwise, if the rescue medication start time is missing and rescue medication start date is equal to the study drug dose date + 1 day, with no eDiary efficacy data recorded the day after dosing, then the imputed rescue medication start date/time is set to the study drug start date/time + upper bound of the 24-hour analysis window (see Table 6).
- Death date: Last contact date (see Section 7.1.3), derived only for subjects who died (see Section 6.4.1.1).

No imputations are performed on these derived dates, except as specifically mentioned in this Section 7.1.5. Complete dates are those with valid, non-missing day, month, and year.

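### The 24-hour rescue analysis drops subjects with an untimed rescue entry dated on the dosing day, although the SAP's own definition already makes them rescue users within 24 hours

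*SAP*

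**What the plan says.** The endpoint in SAP Table 2, objective 6, is the percentage of treated subjects who use rescue medication within 24 hours of study drug, with all available assessments used.

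SAP 6.3.3.6 takes its definition of rescue from SAP 6.2.6.3. There, an entry on the Rescue Medication CRF with a complete date qualifies on the date alone when a clock time is lacking: "medication date is on or after study drug start date if the medication time or study drug start time is missing". An untimed entry dated on the dosing day is therefore a rescue medication.

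SAP 6.3.3.6 then removes subjects with a "rescue medication start date on or before study drug start date/time + 24 hours and missing rescue medication start time are excluded". The one override is "if a subject has at least one rescue medication use with non-missing start time" that falls within 24 hours of dosing; that subject stays in and is a failure.

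Two other sections deal with the same record:

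- SAP 6.3.3.3 (pain freedom at 2 hours): "If the time of first rescue medication is missing, subjects are considered as failures if the date of rescue medication is the same" as the dosing date.
- SAP 7.1.5 (time-to-event analyses): for an untimed entry on the dosing date, "the imputed rescue medication start date/time is set to the study drug dose date/time".

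For this endpoint Protocol 9.4.5 says "there will be no imputation for missing data, the analysis will be based on non-missing, observed data". Protocol 6.4.2 says that "use of rescue medication is recorded by the subject in a paper diary".

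**The concern.** A subject whose only rescue record within 24 hours is an untimed entry on the dosing day is, by the SAP's definition, someone who took rescue after dosing on that day. That settles the 24-hour question without a clock time. The exclusion nevertheless takes the subject out of both numerator and denominator.

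Among dosing-day entries the rule can remove only events, so it lowers the reported rescue rate in any arm where it operates and where some subjects did not use rescue. It also leaves outputs that do not reconcile: a subject can be a rescue failure at 2 hours in one table and be absent from the table of rescue by 24 hours.

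At stake are the reported rates, the stratified risk difference and its confidence interval for one of six secondary endpoints. SAP section 5 says significance will not be evaluated, so no test decision depends on it. Paper recording makes a blank clock time plausible, and the SAP writes several rules for that case.

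The point is confined to entries dated on the dosing day. Untimed next-day entries and missing or partial dates can be undetermined at 24 hours.

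**Working it through.** **Inputs.** Planned treated number per arm: 80 (Protocol 9.2, SAP section 5). Rescue rate and frequency of missing times: not in the documents, so the values below are assumptions.

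**The plan's own figure.** The only stated design figure is roughly 88% power on the primary endpoint. With difference 1.5, SD 3.0, 80 per arm and two-sided alpha 0.05, the normal approximation gives 88.5% and the noncentral t with 158 df gives 88.2%. It reproduces, but nothing here depends on it beyond the 80 per arm.

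**Step 1: does the date settle 24-hour status?** Let the dose be at minute d of the day, d = 0 to 1439. The latest post-dose minute on the same date is 1439, so elapsed time is at most 1439 − d, and its maximum is 1439 minutes (d = 0). This is below 1440 for every d. Once the entry is classed as post-dose rescue, it lies within 24 hours.

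For an untimed entry dated the next day, the latest elapsed time is 2879 − d. This exceeds 1440 for 1439 of the 1440 dosing minutes, so status there is usually unknown. The argument stops at the dosing day.

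**Step 2: effect on one arm.** With x rescue users among n, of whom k have only an untimed dosing-day entry, the reported rate is (x − k)/(n − k). This is below x/n whenever k > 0 and x < n. Assume 32/80 = 40.0%:

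| k | Reported | Rate |
|---|---|---|
| 1 | 31/79 | 39.2% |
| 2 | 30/78 | 38.5% |
| 4 | 28/76 | 36.8% |
| 8 | 24/72 | 33.3% |

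In a smaller set each record weighs more: 12/30 = 40.0% becomes 10/28 = 35.7% with k = 2.

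**Step 3: effect on the difference (rimegepant − placebo).** Assume a true 20/80 vs 32/80, that is −15.0 points:

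| k rimegepant, placebo | Reported | Difference (points) |
|---|---|---|
| 4, 4 | 16/76 vs 28/76 | −15.8 |
| 2, 4 | 18/78 vs 28/76 | −13.8 |
| 0, 4 | 20/80 vs 28/76 | −11.8 |
| 4, 0 | 16/76 vs 32/80 | −18.9 |

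At higher rates, 48/80 vs 60/80 (−15.0), k = 4 and 4 gives 44/76 vs 56/76 = −15.8.

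Expressed as a share u of rescue users rather than a count, the reported rate is p(1 − u)/(1 − pu). At 30% vs 50% (−20.0), u = 0.10 in both arms gives 27.8% vs 47.4% = −19.5, and u = 0.10 vs 0.20 gives −16.6. At 40% vs 40%, u = 0.10 vs 0.20 gives a spurious +2.7 points.

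**Scale.** The 95% half-width at 20/80 vs 32/80 is 1.96 × √(0.25×0.75/80 + 0.40×0.60/80) = 14.3 points.

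**The case against.** The strongest reply is that the second branch of SAP 6.2.6.3 is an inclusive default, applied exactly when the order of dose and tablet cannot be seen. Before the qualifying attack subjects may take the same drugs for milder pain, and one paper diary holds both kinds of use. An untimed dosing-day entry may therefore be a pre-dose tablet, and counting all of them could overstate the rate. As a matter of fact this stands: these subjects are events under the SAP's convention, not by direct observation of timing. It does not rescue the rule, because 6.3.3.6 adopts that convention and then reopens the doubt in this analysis alone.

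Second, the exclusion looks deliberate: the protocol allows no imputation for this endpoint, and SAP 6.3.1 is expressly disapplied. But the complete date is observed data and settles 24-hour status, so no time has to be imputed. Setting 6.3.1 aside leaves the 6.2.6.3 definition in force.

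Third, 6.3.3.3 and 7.1.5 are conservative conventions for endpoints where rescue is an intercurrent event, and 7.1.5 is limited to time-to-event analyses. That is fair. They show inconsistent treatment of one record; the argument itself rests on 6.2.6.3.

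Fourth, the effect may be small. With four exclusions in each arm the assumed difference moves 0.8 points against a half-width of 14.3. Larger shifts need missing times to be unbalanced between arms, for which a double-blind trial gives no particular reason, or to be common. This stands and bears on priority. The n/N display would reveal the total excluded, but not the reason.

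**Conclusion.** The concern holds for untimed entries dated on the dosing day. Under the definition that 6.3.3.6 itself adopts, these subjects are rescue users within 24 hours, and excluding them biases each affected arm's reported rate downward. The risk difference can move in either direction.

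The size cannot be fixed from the documents. In the assumed cases with 80 per arm, one to eight such subjects lower a 40.0% rate by 0.8 to 6.7 points (40.0 − 39.2 and 40.0 − 33.3). A −15.0-point difference ends between −11.8 and −18.9, the extremes being four exclusions in one arm and none in the other. SAP section 1 records early termination for low enrollment; if the treated set is small, each exclusion counts for more. The conclusion rests on the 6.2.6.3 convention that an untimed dosing-day entry is post-dose. It concerns estimation only, and it should be corrected because the inconsistency is clear and cheap to remove.

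**What to change.** In SAP 6.3.3.6, state that a subject with an untimed Rescue Medication CRF entry dated on the dosing date is counted as a rescue user within 24 hours. Limit exclusion to untimed entries dated the next day, and to missing or partial dates, where 24-hour status cannot be determined. Keep the existing override for subjects with a timed use within 24 hours. Report the number excluded per arm.

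The cost is one sentence in the SAP and a small programming change. No clock time is imputed, so the change stays consistent with Protocol 9.4.5.
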